## 9.4 STATISTICAL ANALYSES

Data will be analyzed as means with standard deviations. All hypothesis-testing derived analyses will utilize an alpha of 0.05, beta of 0.8, and utilize two-tailed tests.

### 9.4.1 ANALYSIS OF THE PRIMARY EFFICACY ENDPOINT(S)

For all endpoints (Tinnitus loudness, TFI and THI), the following approach will be utilized. All measures are ordinal, repeated measures. Final analysis will occur after unblinding.

Tinnitus loudness is measured by having subjects match the loudness and likeness of their tinnitus to one of 11 sounds with different center frequencies. Absolute differences are averaged relative to baseline to determine loudness. TFI and THI are questionnaires to be completed at each weekly visit. Both are measured on an interval scale. See section 3.1 for more details

A General Linear/Logistic Mixed (GLLM) effects analytic model will be used. GLLM is considered ideal when analyzing repeated measures as it treats time as a continuous variable and can account for missing data. This framework can readily adapt to subgroupings present in the data. GLLM analysis includes random and fixed effects. In this study, treatment order (active first vs sham first), treatment condition (active, active washout, sham, sham washout), baseline loudness, baseline TFI, and interaction of treatment and treatment order are treated as fixed while intercept is treated as a random effect.

Adjustments for Type I error over the set of endpoints is unnecessary as the measures are not directly related.

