### 1.3 SCHEDULE OF ACTIVITIES (SOA)

period		Arm 1		End Period 1	Washout	Arm 2		End Period 2	Washout	EOS	Post-study monitoring Weeks 28, 32, 36
visit	Screening	Baseline 1	End of weeks 1-5	End of week 6	End of week 7-11	End of week 12/Baseline 2	End of weeks 13-17	End of week 18	End of week 19-23	End of week 24	32, 36
day		Day 0	Days 7, 14, 21, 28, 35	Day 42	Days 49- 84	Day 91	Days 98, 105, 112, 119, 126	Day 133	Days 140- 168	175	252
window			'+ or - 3 days, but 5 days between weekly visits	'+ or - 3 days, but 5 days between weekly visits	'+ or - 3 days, but 5 days between weekly visits	'+ or - 3 days, but 5 days between weekly visits	'+ or - 3 days, but 5 days between weekly visits	'+ or - 3 days, but 5 days between weekly visits	'+ or - 3 days, but 5 days between weekly visits	'+ or - 3 days, but 5 days between weekly visits	'+ or - 3 days, but 5 days between weekly visits
	Informed Consent	x									
	Medical History	x									
	Tinnitus Maneuver Checklist	x		x	x			x		x	
	Audiogram	x	x	x	x	x	x	x	x	x	
	TFI	x	x	x	x	x	x	x	x	x	x
	THI	x	x	x	x	x	x	x	x	x	
	TinnTester	x	x	x	x	x	x	x	x	x	
	THS	x		x		x		x		x	
	MMI	x		x		x		x		x	

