### 3.2 SECONDARY MEASURES

1) Tinnitus bandwidth/spectrum: Near its start the TinnTester software asks subjects to indicate which of three sounds best resembles their tinnitus; 5 kHz pure tone ("tonal" tinnitus), a narrow band noise centered at 5 kHz ( $\pm 5\%$  of CF, BPN5 masker, "ringing" tinnitus), or a wider band of noise centered at 5 kHz ( $\pm 15\%$  of CF, BPN15 masker, "hissing" tinnitus). We will relate treatment outcomes to tinnitus bandwidth by these measurements. We will also be able to determine whether the treatment alters bandwidth.

2) Minimum Masking Level (MML): Subjects adjust the level of the 5 kHz BPN15 sound until they can no longer hear their tinnitus. MML may prove sensitive to the bimodal treatment procedure. MML should be reduced, if tinnitus assessed by loudness matching is also reduced. However, even when tinnitus loudness is reduced, there are subjects for whom tinnitus cannot be masked.

3) Tinnitus Hearing Survey: A brief nine question survey which determines self-perceived handicap due to tinnitus, hearing loss, and hyperacusis. This questionnaire differs from the two primary questionnaires in that it qualifies any perceived handicap due to hearing loss and/or sound sensitivity (hyperacusis).

OBJECTIVES	ENDPOINTS	JUSTIFICATION FOR ENDPOINTS
Primary		
1) Objective Tinnitus loudness (TinnTester)	1) End of 1 st arm 2) End of first washout 3) End of 2 nd arm 4) End of second washout	To determine how use of device affects objective tinnitus loudness before and after the treatment and sham arms of the study.
2) Tinnitus Functional Index	1) End of 1 st arm 2) End of first washout 3) End of 2 nd arm 4) End of second washout	To determine how use of device affects the tinnitus and quality of life before and after the treatment and sham arms of the study
3) Tinnitus Handicap Index	1) End of 1 st arm 2) End of first washout 3) End of 2 nd arm 4) End of second washout	To determine how use of device affects the tinnitus and quality of life before and after the treatment and sham arms of the study
Secondary		
1) Tinnitus bandwidth/spectrum (TinnTester)	1) End of 1 st arm 2) End of first washout 3) End of 2 nd arm 4) End of second washout	To determine how use of the device may or may not change the perceived frequency (spectra) of tinnitus following the treatment or sham arms.

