### 6.1.2 DOSING AND ADMINISTRATION

Each subject will have their tinnitus spectrum assessed with the Tinn Tester protocol (L. Roberts et al, 2008). This spectrum is digitized and programmed into the device as the signal to be delivered to the subject. The amplitude is limited to 95 dB SPL and is delivered together with an electrical stimulus delivered a short time after the auditory stimulus (as determined by the preclinical studies). This stimulus is presented by the device when the subject turns on the device. The device limits the time of presentation to 30-60 min per day.

This protocol is presented once a day for 30-60 minutes for 6 weeks. After that there is a washout period of 6 weeks in which no device is used. Subjects are tested once a week to assess the primary and secondary outcomes and when baseline is achieved. The second arm of the study begins for another 6 weeks. A second washout of 6 weeks occurs, end of study visit, and 12 weeks of follow up, after which the subject participation is ended. Completion of Arm 1 and Arm 2 do not necessarily have to be consecutive, and we will allow for 12 weeks in between in order to provide more flexibility for subjects. The dose will not change over the course of the study. Maximum duration of enrollment is 36 weeks.

The subjects will be trained on how to use the devices and place the earphones and electrode pads. Once they have been effectively trained, subjects will take the devices home to use for the 30-60 min/day periods. Once a week the primary and secondary outcomes will be tested along with any review or questions that the subjects need to be answered. Subjects are asked to use the device at the same time every day but If subjects miss a treatment they are instructed to use it at another time rather than miss that treatment.

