### 6.4 STUDY INTERVENTION COMPLIANCE

The devices are electronic monitoring compliant – successful daily use is registered, also detects and records open circuits or failures. Primary and secondary outcomes are measured weekly and recorded by study team members electronically on secure databases.

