## 9 STATISTICAL CONSIDERATIONS

### 9.1 STATISTICAL HYPOTHESES

The data will be collected throughout the course of the study by blinded test administrators. A General Linear/Logistic Mixed (GLLM) effects analytic model was developed in consultation with UM statistics department prior to our preliminary trial. GLLM is considered ideal when analyzing repeated measures as it treats time as a continuous variable and can account for missing data. This framework can readily adapt to subgroupings present in the data. GLLM analysis includes random and fixed effects. In this study, treatment order (active first vs sham first), treatment condition (active, active washout, sham, sham washout), baseline loudness, baseline TFI, and interaction of treatment and treatment order are treated as fixed while intercept is treated as a random effect. All metrics are computed relative to baseline for each subject.

MICHR has provided templates, tools, and general guidance in support of activities conducted by the study team to facilitate study and data management, and will continue to do so. The University of Michigan's Department of Statistics Consulting for Statistics, Computing and Analytics Research (CSCAR) has provided individualized support and training to our team on management, collection, and analysis of data for phase 1 (which is identical to the second except in terms of subject numbers and treatment duration). Staff are available for continued support in the use of technical software, and advanced computing in research.

- Primary Efficacy Endpoint(s):
  - 1) Objective Tinnitus Loudness
  - 2) Tinnitus Functional Index
  - 3) Tinnitus Handicap Index
- Secondary Efficacy Endpoint(s):
  - 1) Tinnitus bandwidth/spectrum
  - 2) Minimum masking level
  - 3) Tinnitus Hearing Survey

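### The primary mixed model names only a random intercept and does not settle whether weekly or end-of-phase readings are fitted; if weekly, the active-minus-sham standard error may be too small, and the stated power belongs to a different model

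*Combined protocol and SAP*

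**What the plan says.** **Model.** Section 9.4.1, repeating section 9.1, lists as fixed effects treatment order, a four-level condition (active, sham and the washout after each), baseline loudness, baseline TFI and a treatment-by-order term. On the random part it says: "interaction of treatment and treatment order are treated as fixed while intercept is treated as a random effect". No residual covariance, subject-by-phase effect or robust standard error is named. Section 9.1 adds: "All metrics are computed relative to baseline for each subject".

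**Which readings.** Section 6.1.2: "Once a week the primary and secondary outcomes will be tested". Section 6.4: "Primary and secondary outcomes are measured weekly". The schedule in section 1.3 has treatment-phase visits at "Days 7, 14, 21, 28, 35" plus day 42, so six per treatment phase. Section 9.4.1 itself says "TFI and THI are questionnaires to be completed at each weekly visit" and favours the model because "it treats time as a continuous variable and can account for missing data". No time term appears among its effects. The table in section 3.2, however, gives each primary outcome four time points: the end of each arm and of each washout. Its stated aim for loudness is "To determine how use of device affects objective tinnitus loudness before and after the treatment and sham arms of the study".

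**Missing data.** Section 9.3 handles missing values and losses to follow-up by last observation carried forward.

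**Sample size.** Section 9.2 compares simulated slopes by ANCOVA, claims independence from baseline normalisation, and uses 50 runs per size. It reports 14 per arm for loudness, 17 per arm for TFI, 34 in total, and a minimum of 50.

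**The concern.** A random intercept absorbs what is constant within a subject across the whole study. It cancels from active minus sham, so it does not protect that contrast. What matters there is correlation specific to a phase: a subject who runs high or low for several weeks together. If six weekly readings per phase are fitted with independent residuals, they count as six independent pieces of information about that phase. Where they are correlated, the standard error, p-value and confidence interval are too optimistic. More subjects do not help, because the true and the reported variance shrink together.

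With one reading per phase the difficulty nearly vanishes. Whether the primary test holds its 5% level therefore turns on a choice that the plan leaves open. The same choice decides whether the reported effect is a phase average or an end-of-arm effect: section 3.2 points to end of arm, while the four-level condition fitted to weekly data would give a phase average. The stated power cannot be carried over to the planned model in either case.

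**Working it through.** **Inputs.** Six readings per phase and four phases (section 1.3, by week labels); random intercept only (sections 9.1 and 9.4.1); two-sided 5% level (section 9.4). The within-phase correlation r left after the subject intercept is an assumption, because the documents give none. Independent residuals are also an assumption: they are the usual default when nothing is specified.

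**1. The plan's own figure.** 2 × 17 = 34 reproduces. The 14 and 17 cannot be reproduced, because the pilot slopes, residual variance and correlation are not given. The Monte Carlo standard error of a simulated power of 0.80 is sqrt(0.8 × 0.2 / 50) = 0.057, or 5.7 points; with 1,000 runs it is 1.3 points.

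**2. Weekly readings, random intercept only.** Set the within-subject variance of one reading to 1.
- The true variance of a six-reading phase mean is (1+5r)/6.
- The model pools 3 between-phase and 20 within-phase degrees of freedom per subject. Its residual variance is [3(1+5r) + 20(1−r)]/23 = 1 − 5r/23.
- True over reported variance of active minus sham is therefore (1+5r)/(1−5r/23). The number of subjects does not appear.
- Actual rejection rate under the null is 2Φ(−1.96/√ratio).

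| r (assumed) | Variance ratio | Correct CI width / reported | Rejection at nominal 5% |
|---|---|---|---|
| 0 | 1.00 | 1.00 | 5.0% |
| 0.05 | 1.25/0.989 = 1.26 | 1.12 | 8.1% |
| 0.1 | 1.50/0.978 = 1.53 | 1.24 | 11.3% |
| 0.3 | 2.50/0.935 = 2.67 | 1.64 | 23.1% |
| 0.5 | 3.50/0.891 = 3.93 | 1.98 | 32.3% |

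If only the two treatment phases are fitted, the divisor is 1 − 5r/11 and the rates are 5.0, 8.3, 11.8, 24.9 and 35.7%. With serial AR(1) correlation instead, at weekly lag 0.1, 0.3 and 0.5, they are 7.3, 13.4 and 21.9%. Null simulation with the treatment-by-order term fitted (20,000 datasets per setting at 34 and 50 subjects, 10,000 at 100) agrees within 0.8 points.

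**3. End-of-phase readings only.** The same model gives 4.8–5.0% for r from 0 to 0.5. At AR(1) 0.3, 0.5, 0.7 and 0.8 it gives 5.0, 5.1, 5.6 and 6.2%.

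**4. Carry-forward alone** (r = 0, 50 subjects, one missed visit per affected phase filled from the previous reading). Rejection is 5.1–5.4% if 10% of phases are affected, 5.8–6.0% at 25%, 6.7–7.1% at 50% and 8.7–8.8% at 100%. Losses to follow-up were not modelled.

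**5. Do the repairs work?** A subject-by-phase random effect gives 4.8–5.3% for r from 0 to 0.5 (exact balanced REML, 50 subjects). Under AR(1) 0.3–0.8, where correlation crosses phase boundaries, it gives 5.6–7.9%. Testing each subject's active-minus-sham difference in phase means, adjusted for order, gave 4.5–5.5% in every setting tried.

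One caution: 139 fits of the subject-by-phase model in general mixed-model software at r = 0.1 gave 10.1%, with many convergence failures. Exact REML gave 8.6% on the same datasets and 5.0% on 20,000 fresh ones, so the larger run is used.

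**6. Section 9.2 against section 9.4.1.** The power simulation compares slopes over time; section 9.4.1 lists condition levels and no slope. Subtracting a subject's baseline cannot make that subject's readings independent, since all of them share it. The simulation sums two arms, although section 4.1 has every subject in both. It also omits THI, the third primary endpoint.

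**The case against.** The best defence is that section 3.2 is the only place that assigns time points to the primary endpoints, and it assigns end of phase, the reading for which the standard error is sound. Weekly measurement has a purpose of its own in the safety checks of sections 7.1 and 8.2. Section 9.4.1 is silent on residual covariance; it does not specify independence. No correlation is given either. The remark in sections 7.1 and 8.2 that outside stressors can move TFI does not say that they persist within a phase, and it concerns TFI only.

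All of this stands, and it makes the inflation conditional. It does not remove the conflict, because the analysis section itself refers to weekly completion and continuous time. A reader might infer that the primary tests will reject a true null up to a third of the time. The documents do not support that: it needs weekly fitting, independent residuals and an assumed r near 0.5 together.

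A reader might also infer that 34 or 50 subjects are too few. That does not follow. Ignoring the pairing is, taken alone, conservative, and 50 already exceeds 34. If week-by-condition terms were added, the primary test could also compare slopes; the pairing, the independence claim, the missing THI and the 50 runs would still separate it from section 9.2.

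Nor does the absence of baseline THI from the covariates harm the contrast. A covariate constant within subject cancels from active minus sham in balanced data, and a trial fit gave the same estimate and standard error with and without it.

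Finally, the carry-forward effect is small for isolated missed visits.

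**Conclusion.** The point holds as an unreconciled specification with a conditional consequence. What is firm is that the plan names one random effect and no residual covariance, and that sections 3.2 and 9.4.1 point to different readings. The size of any inflation is not firm. With weekly readings and independent residuals, the rejection rate is about 8, 11, 23 and 32% at assumed r of 0.05, 0.1, 0.3 and 0.5; with end-of-phase readings it is about 5 to 6%.

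Carry-forward would enter copied values as new readings, although section 9.4.1 says the model can deal with missing data. The effect is about 5–7% unless most phases are affected.

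The 0.8 power behind 14, 17 and 34 is not the power of the contrast in section 9.4.1. Whether the true figure is higher or lower cannot be told from the documents. This should be fixed, because whether the primary tests hold their level depends on it and the repair is cheap.

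**What to change.** Before unblinding, amend section 9.4.1 and bring it into line with section 3.2:

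- State which readings enter the primary model.
- If weekly, add a subject-by-phase random effect or a within-phase residual covariance, or test each subject's active-minus-sham difference using one value per phase. The last is the safest against serial correlation across phases and avoids convergence trouble.
- State whether week and week-by-condition terms are included, so that the contrast matches the intended endpoint, phase mean or end of arm.
- Fit observed values in the primary model and keep last observation carried forward as a sensitivity analysis.
- Re-run the power simulation on that crossover model for loudness, TFI and THI with at least 1,000 replicates, and restate 14, 17 and 34.

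The cost is SAP wording and a few hours of simulation, with no extra patients. Confidence intervals may be wider and the restated power may differ.

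The choice of endpoint has a price of its own. If the effect builds linearly from zero, the signal-to-noise of the single week-6 reading relative to the six-week mean is sqrt((1+5r)/6)/(3.5/6): 0.70 at r = 0, 0.86 at 0.1 and 1.31 at 0.5. If the effect is constant from week 1, it is sqrt((1+5r)/6), or 0.41 to 0.76 over the same range. That choice is the sponsor's.

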### 6.3 MEASURES TO MINIMIZE BIAS: RANDOMIZATION AND BLINDING

Subjects are randomly assigned to group 1 (active first, then sham) or group 2 (sham first, then active) using Matlab's *randsample* command with a predetermined, fixed, secret seed value. *Randsample* generates random numbers using the Mersenne twister algorithm. We will enroll subjects in a 1:1 ratio to create a balanced study design. To ensure blinding, group assignment is generated *in silico* and assignment programmed into each device, without the intervention of a study member. This parameter is not made accessible to study members without password authorization. Devices are encrypted to prevent study team members or subjects from accessing device data in an unauthorized manner.

As the randomization list is generated algorithmically, the code can be reproduced with knowledge of the secret seed value. Unblinding may occur at the end of the study or in the case of an SAE related to the study (worsening of tinnitus, worsening of hearing threshold). Study investigators that do not have contact with subjects may unblind. Intentional and unintentional unblinding must be reported to the principle investigator.

Imperfect blinding could arise from the presence of the electrical stimulation present during active treatment. To avoid unblinding, subjects will be told that they may or may not feel electrical stimulation during both phases of the study. The previous study suggested that subjects tend to acclimate to the presence or lack of electrical stimulation during a day's treatment. Subjects will be discouraged from divulging whether they can feel the electrical stimulus.

No investigators are allowed to remain unblinded for the duration of the study. All analyses that could require unblinding (SAEs, worsening of a subject's tinnitus/hearing) will be identified by software, and the investigators notified by automated communication methods.

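### The primary model has a treatment-by-order interaction, no period term and no named contrast: in this crossover the interaction is period plus average carry-over, and the tested estimate is left open

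*Combined protocol and SAP*

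**What the plan says.** Section 6.3 sets up a two-order, two-period crossover: "Subjects are randomly assigned to group 1 (active first, then sham) or group 2 (sham first, then active"). Allocation is equal: "We will enroll subjects in a 1:1 ratio to create a balanced study design".

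Sections 9.1 and 9.4.1 give the same list of model terms for loudness, TFI and THI. Besides treatment order, the fixed effects are "treatment condition (active, active washout, sham, sham washout), baseline loudness, baseline TFI, and interaction of treatment and treatment order are treated as fixed". The only random effect is the intercept: "interaction of treatment and treatment order are treated as fixed while intercept is treated as a random effect".

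Period is not in the list. Section 9.4.1 says of the model class that "it treats time as a continuous variable and can account for missing data", but time is not among the listed effects either. Section 9.1 adds: "All metrics are computed relative to baseline for each subject". Neither section states the factor coding, the reference level, which contrast among the four conditions is the primary test, or how the interaction will be used. Section 9.4.1 places the final analysis after unblinding.

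**The concern.** A crossover is chosen so that changes common to all subjects over time cancel out of the treatment comparison. Such changes are plausible here. The Schedule of Activities puts the second baseline at day 91, section 6.1.2 allows 12 weeks between arms, and section 7.1 accepts that TFI can respond to life events unrelated to treatment.

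Two things can go wrong with the model as listed. First, an interaction between treatment and order invites the reading that treatment works differently by order, when ordinary drift alone would produce it. Second, once the interaction is in the model, the main-effect coefficient for treatment depends on coding. In one common coding it describes a single order group and carries the period shift. Two analysts who follow section 9.4.1 exactly could report different estimates, standard errors and p-values from the same data.

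**Working it through.** **Inputs from the documents.** Two orders, 1:1 (section 6.3). Model terms (sections 9.1 and 9.4.1). Two-sided alpha of 0.05 (section 9.4). Seventeen subjects per arm for TFI, total 34, minimum proposed 50 (section 9.2). At 50 subjects, 1:1 allocation gives 25 per order.

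**The plan's own figure.** 2 × 17 = 34 checks. The 17 cannot be reproduced, because section 9.2 gives no slope, effect size or SD.

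**Assumed, because the documents give no value.** The period shift p is expressed in units of the SD of the within-subject active-minus-sham difference, and a range is shown.

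**Step 1: what the interaction is.** Let τ be the treatment effect, p the shift from first to second arm, and λA and λS the carry-over from active and from sham.
- Active-first group: active minus sham = τ − p − λA
- Sham-first group: active minus sham = τ + p + λS
- Half the difference between groups (the interaction) = p + (λA + λS)/2
- Equal-weight mean of the groups = τ − (λA − λS)/2

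The interaction is therefore period plus average carry-over. The averaged contrast is free of p, and equals τ if carry-over is the same from both treatments.

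A design-matrix check agrees. For the four active/sham cells, the effect-coded treatment-by-order column is identical to the period column, and the rank stays 4 when period is added. For all eight order-by-phase cells the rank stays 8. Adding period while keeping the full interaction changes nothing.

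**Step 2: what the treatment coefficient is, without carry-over.**
- Reference coding, active-first as reference: τ − p
- Reference coding, sham-first as reference: τ + p
- Sum-to-zero coding, or averaging over orders: τ

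Simulated cell means with τ = −1 and p = −0.5 (in units of the simulated outcome) gave −0.49, −1.51 and −1.00.

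Random-intercept fits at 50 subjects, with τ = 0 and p = −0.5 in outcome units, six weekly values per phase, and between-subject and residual SD both 1 (assumed; means of 40 fits):

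| Model | Estimate | SE |
|---|---|---|
| Planned terms, reference active-first | +0.50 | 0.115 |
| Planned terms, reference sham-first | −0.50 | 0.115 |
| Planned terms, sum-to-zero order coding | −0.00 | 0.082 |
| Order + condition + period, no interaction | −0.00 | 0.082 |
| Planned terms, reference active-first, plus linear week | +0.46 | 0.23 |

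**Step 3: type I error if the one-order coefficient is tested.** With the SD of the difference set to 1, its SE is 1/√25 = 0.20, against 1/√50 = 0.141 for the averaged contrast: a ratio of √2 = 1.41. With τ = 0, the test statistic is non-central t on 48 df with non-centrality p/0.20.

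| Assumed p (SD of difference) | Non-centrality | One-order coefficient | Averaged contrast |
|---|---|---|---|
| 0 | 0 | 5% | 5% |
| 0.2 | 1.0 | 16.5% | 5% |
| 0.3 | 1.5 | 31% | 5% |
| 0.5 | 2.5 | 69% | 5% |

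**Step 4: power with no period shift.** Take the effect for which the averaged contrast has 80% power at 34 subjects: (1.960 + 0.842)/√34 = 0.480.
- Averaged contrast, 50 subjects: Φ(0.480 × √50 − 1.96) = 0.92
- One-order coefficient, 25 subjects: Φ(0.480 × √25 − 1.96) = 0.67

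**The case against.** A reader might infer that the plan fails to adjust for period and that its treatment estimate is therefore confounded with it. The documents do not support that. The planned terms span period, so the fitted means already allow for it. Confounding arises only if the factors are reference-coded and that one coefficient is the test, and the plan says neither. With sum-to-zero coding or an order-averaged contrast, the planned model gives the same estimate and SE as a model with an explicit period term. This part of the objection stands, and it makes every figure in step 3 and the 67% in step 4 conditional.

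The period shift is also assumed. If responses in the second arm are measured from Baseline 2, drift already present by then is subtracted and p may be small. Section 9.1 does not say which baseline applies, so the size of p cannot be settled either way.

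A reader might also infer that power falls to about 50%. That follows only if the effect is set to give 80% power at 50 subjects. Section 9.2 puts 80% at 34 and treats 50 as a margin, which gives about 67%.

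Finally, it could be said that time as a continuous variable covers the matter. Time is not a listed effect, and a linear week term did not rescue the reference-coded coefficient when the shift was a step.

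The objection does not answer two things: the interaction has no valid reading as an order-dependent treatment effect, and the plan does not say which quantity will be tested.

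**Conclusion.** The concern holds as a defect of specification and interpretation, not as proof of a biased analysis. For active versus sham, the listed interaction is period plus average carry-over. The primary contrast is not named, and one ordinary way of fitting the listed terms gives τ − p or τ + p with an SE 1.41 times larger.

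Under that reading alone, and for assumed shifts of 0.2 to 0.3 SD of the within-subject difference, type I error is about 16.5% to 31% instead of 5%. With no shift, power at 50 subjects is about 67% instead of 92%, for an effect that the averaged contrast detects with 80% power at 34. Under an order-averaged contrast there is no inflation and no loss. Because the choice would otherwise be open after unblinding, it should be settled before then.

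**What to change.** In sections 9.1 and 9.4.1, state that the primary test for each endpoint is the one-degree-of-freedom active-minus-sham contrast, averaged with equal weight over the two orders. Then do one of the following:

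- Replace treatment-by-order with a fixed period effect (first versus second arm, and first versus second washout), keeping order.
- Keep the planned terms and state that the active/sham part of the interaction represents period and carry-over, not a differential treatment effect.

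Show the order-specific differences as description only.

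The cost is a few sentences and no new data. The first option is not quite the same model. With four conditions the planned terms use 1 + 1 + 3 + 3 = 8 mean parameters for eight cells, and the replacement uses 1 + 1 + 3 + 2 = 7. Both options still assume no differential carry-over, and the text should say so.
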